#### 7.3 Randomisation Method and Procedure

Once the biopsy sample has been received by the central laboratory, patients will be stratified into 2 groups, CD80/CD86 positive (biomarker+) or CD80/CD86 negative (biomarker-) and randomised 1:1 to receive either abatacept and methotrexate therapy or placebo and methotrexate therapy.

Randomisation will take place when all the screening procedures and the biopsy visit are complete, and the biopsy has been received by the central laboratory.

The local site staff (Principal Investigator/research nurse) must log in to the secure 24-hour/7 day automated Early RA 3TR database for the 3TR-PARTNER-RA study (https://era3tr.whri.qmul.ac.uk) with the Data Safe Heaven (ITS) as backup and complete Screening and Biopsy visit (visits 1 and 2) electronic CRFs prior to randomisation. In the rare event that the 3TR-PARTNER-RA database (Early RA 3TR) is not accessible, paper CRFs may be submitted to perform the randomisation. The 3TR-PARTNER-RA Trial Office will then confirm eligibility and perform randomisation.

The Coordinating Trial Office will then confirm eligibility based on the data recorded, and once the result of the biopsy analysis has been received from the central laboratory the randomisation will be performed.

The randomisation in the study will be applied using simple randomisation by the 3TR Trials office, with an equal allocation ratio. All patients with sufficient RNA for analysis will be randomised using simple randomisation (1:1 allocation ratio) into the drug or placebo arm according to biomarker arms (positive or negative biomarker).

The randomisations list will be prepared by the Trial Statistician and securely stored in a separate table within the Early RA 3TR database back-end so that it is not accessible to end users or anyone else than a limited number of information support staff who have access to all systems. Once a participant has been allocated an arm, there is an audit trail that prevents anyone from changing the allocation or pretending that no allocation has been made.

Before the study is initiated, the log-in details, telephone number and call-in directions for the Early RA 3TR Database for the 3TR-PARTNER-RA study will be provided to each site.

The randomized intervention kit number list is generated centrally by BMS and IMPs are packaged in accordance with this list. The randomization and intervention allocation are performed centrally by the Early RA 3TR Database, which generates the participant randomization list and allocates the intervention number and the corresponding intervention kits to the participants according to it.

A randomized participant is defined as a participant who has been allocated to a randomized intervention regardless of whether the intervention kit was used or not (ie, participants registered by the Early RA 3TR Database in the 3TR-PARTNER-RA study). A participant cannot be randomized more than once in the study.

The result (i.e. randomised treatment arm) will then be filled to the local site staff (each site will have a nominated joint assessor). The local site staff will immediately be able to see the result of the randomisation, however, they will be blinded to any information about the patient's biopsy result.

Randomisation methods and procedures will be described within the Database User Manuals and Data Management Plan.

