## 14.0 Statistical and data analysis

#### 14.1 Sample size calculation

The primary analysis of the trial is the comparison between Group 1 and Group 3 (see figure in Section 2.6), i.e. the patients classified as biomarker positive treated with Abatacept + Methotrexate (MTX) (Group 1) vs. the patients classified as biomarker negative treated with Abatacept + Methotrexate (MTX) (Group 3). Since patients will be randomised 1:1 to either Abatacept + MTX or Placebo + MTX and the median value observed in the PEAC study as a cut-off to classify the biomarker status, we expect the comparison groups to be roughly equal. That would allow to ascribe the differences in response we will observe to the different biomarker profiles of the two groups, hence demonstrating if the presence of a biomarker will enhance the response to the any of the drugs included in the trial.

The power calculation is done for this comparison, based on the following assumptions:

50% patients will be classified as biomarker positive and 50% as biomarker negative
 Using change in CDAI score from baseline (delta CDAI) as the primary outcome, a difference in delta CDAI between the two comparison groups of 10, with a Standard Deviation of 14.34. These are the values that were observed when analysing the difference in delta CDAI between biomarker positive and biomarker negative patients treated with MTX in the PEAC study. Although PEAC patients were not treated with Abatacept, this comparison is expected to be even more in favour of the biomarker positive group using Abatacept together with MTX. Thus, basing the power calculation on the PEAC observed difference is a conservative assumption.

With these assumptions, 88 patients would be needed to detect a significant difference of 10 in delta CDAI with 90% power (66 patients for 80% power). Since this would only be for Group 1 and Group 3 (44 patients each), a total of 176 patients would be sufficient for 90% power in the whole trial (132 for 80% power) which includes all four groups as per Figure 1 Section 2.6. If we assume a 5% dropout rate and also account for an expected 5% of patients that have insufficient RNA for the Nano-string analysis (based on results from the STRAP trial), 196 patients in the whole trial would be sufficient to detect a significant difference (Group 1 vs Group 3) of 10 in delta CDAI with 90% power (147 patients for 80% power).

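### Simple randomisation after biomarker stratification leaves the number on abatacept, and so the size of the primary comparison, to chance; blocking is a cheap improvement of modest effect.

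*Protocol*

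**What the plan says.** Section 7.3 of the protocol has patients classified as biomarker positive or negative once the biopsy result is in, and then names the allocation method twice: "The randomisation in the study will be applied using simple randomisation", and again "All patients with sufficient RNA for analysis will be randomised using simple randomisation (1:1 allocation ratio) into the drug or placebo arm", by biomarker group. It mentions no blocks, minimisation or cap. Section 5.0 sends procedural detail to a Randomisation Specification form, and section 7.3 to user manuals and the Data Management Plan, but the protocol itself fixes the method as simple.

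Section 14.1 powers the trial on Group 1 v Group 3, both treated with abatacept plus methotrexate. It assumes "a difference in delta CDAI between the two comparison groups of 10", "with a Standard Deviation of 14.34", and that "50% patients will be classified as biomarker positive and 50% as biomarker negative". The whole-trial figure is derived from 88 patients in that comparison: "Since this would only be for Group 1 and Group 3 (44 patients each". The basis for equal sizes is the 1:1 ratio and a cut-off at the median of an earlier cohort, worded as an expectation: "we expect the comparison groups to be roughly equal". Section 14.7 confirms that the primary analysis lies wholly within the abatacept arm.

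**The concern.** Stratified randomisation controls group sizes only if allocation within each stratum is restricted. Under simple randomisation each patient has an independent one-half chance of abatacept whatever the stratum, so the four group sizes have the same distribution as if nobody had been stratified.

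This matters more here than in an ordinary two-arm trial. There, a patient who by chance goes to the other arm is still analysed in the primary comparison. Here, a patient allocated to placebo leaves it. Chance imbalance therefore changes the total number in the primary comparison as well as how it is divided. What is at stake is the spread of realised power around the planned 90%, not the validity of the test.

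**Working it through.** **Inputs.** From section 14.1: difference δ = 10, SD σ = 14.34, biomarker prevalence 50%, 44 per group, 176 evaluable, 5% dropout plus 5% insufficient RNA. Target 200 from section 3.1 and the synopsis. Section 14.1 gives no significance level; two-sided 5% is assumed. It fits the 95% intervals in section 14.7 and reproduces the stated numbers, whereas one-sided 5% would give 36 per group.

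**1. The plan's own figure.** n per group = 2(z₀.₉₇₅ + z₀.₉₀)²σ²/δ² = 2 × (1.960 + 1.282)² × 14.34²/10² = 43.2, rounded up to 44. For 80% power the same formula gives 32.3, so 33. Inflation: 176/0.90 = 195.6, so 196. All agree with section 14.1.

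**2. Power at 44 v 44.** Two-sample t-test with noncentrality δ/(σ√(1/n₁ + 1/n₃)) = 10/(14.34 × √(2/44)) = 3.27 on 86 degrees of freedom: 89.9% (90.5% by the normal approximation).

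**3. Group sizes under simple randomisation, 176 evaluable.**
- Abatacept total: Binomial(176, ½), mean 88, SD √(176/4) = 6.6, 95% range 75 to 101.
- Group 1 or Group 3 with the biomarker split also random: Binomial(176, ¼), mean 44, SD √(176 × ¼ × ¾) = 5.7, 95% range 33 to 55. Both groups reach 44 in 22.5% of randomisations.
- If the biomarker split were exactly 88/88, each group would range over 35 to 53. Mean power would be 89.5% (84.3 to 93.4%).

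**4. Power over the distribution of group sizes.** The power formula of step 2 is evaluated for each possible pair of sizes and weighted by its probability, with a random 50% biomarker split. Blocked allocation is taken as half of each stratum. The rows are the planned minimum (176), 200 recruited with 10% lost (180), and 200 randomised with only 5% dropout (190).

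| Evaluable | Simple: mean power (95% range) | Simple: power below 87% | Blocked: mean power (95% range) |
|---|---|---|---|
| 176 | 89.3% (84.0–93.2) | 16% | 89.5% (88.9–89.9) |
| 180 | 90.0% (84.9–93.7) | 10% | 90.2% (89.6–90.5) |
| 190 | 91.5% (87.0–94.8) | 2.6% | 91.7% (91.1–92.0) |

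Range limits can move by 0.1 point with the method of computation. Under simple randomisation with 176 evaluable, power falls below 80% in about 0.1% of randomisations.

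**5. What blocking does not control.** With 176 evaluable and perfect blocking the abatacept total is held at 87 or 88, but Groups 1 and 3 still range over about 37 to 50 each, because biomarker prevalence varies. Both reach 44 only if the biomarker split is exactly even, a 6% chance. If the smaller biomarker group held 40%, 35% or 30% of 88 abatacept patients (35/53, 31/57, 26/62), power would be 88.6%, 87.1% or 83.9%.

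**The case against.** The strongest reply is that the effect is very small. The average cost of simple randomisation is about 0.4 points of power with an exact 50/50 biomarker split, and about 0.2 against blocking when the split is random. The estimate is not biased, the type I error is unaffected, and ANCOVA is valid with unequal groups. Adjusting for baseline may also leave less residual variance than the unadjusted change-score SD used above. All of this stands, and it is why this is an improvement rather than a defect of validity.

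The margin also matters. The synopsis speaks of 200 randomised patients, and those with insufficient RNA leave before randomisation; on that reading 190 would be evaluable and mean power exceeds 90%. That stands too, so 176 should not be quoted alone.

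A reader might infer that sections 7.3 and 14.1 contradict each other, or that blocking would secure 44 v 44. The documents support neither. Section 14.1 expects only approximate equality, for which 44 is a planning value, and the cut-off comes from another cohort, so the biomarker split is outside the control of any allocation method.

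Finally, blocking adds some predictability. Section 7.7 unblinds each patient after week 16 with an email to the coordinating trial team, section 17.1 has an unblinded monitor, and under section 7.3 the Trial Office both confirms eligibility and performs randomisation. With only two strata, central staff who see past allocations could sometimes guess the next one. The risk is slight, since section 7.3 blinds sites to the biopsy result, section 7.4 provides matched syringes and section 14.2 plans at least 10 centres, but it is not nil and the fix should deal with it.

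**Conclusion.** The point holds as a modest one. Section 7.3 stratifies and then uses a method under which stratification does nothing for group sizes, and the primary comparison bears the full chance variation in the abatacept arm. Mean power stays close to the planned value. What simple randomisation adds is a lower tail: power below 87% in about 16%, 10% or 2.6% of randomisations with 176, 180 or 190 evaluable. It would be wrong to conclude that the trial is underpowered or its result biased. The secondary contrast, (1 minus 2) v (3 minus 4), is hardly touched: its variance rises by about 1% on average.

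These figures rest on the protocol's difference and SD, an assumed two-sided 5% level, a true biomarker prevalence of 50%, and an unadjusted t-test in place of the planned ANCOVA.

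**What to change.** In section 7.3, replace simple randomisation with permuted blocks of randomly varying size within each biomarker stratum, run across sites rather than by site, and bring the Randomisation Specification form into line. State that the list and block sizes are concealed from the Trial Office staff who confirm eligibility and from monitors. This holds abatacept at about half of each stratum. Section 14.1 can keep its wording on approximate equality, since the biomarker split remains uncontrolled.

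The cost is a short change to section 7.3, the matching change to the form and a regenerated list, with no extra patients. The slight predictability for central staff is kept small by the varying block sizes and the concealment.

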# 1.3 Assessment and management of risk

Subjects eligible to take part in the study will be randomised to either abatacept or placebo, both in combination with methotrexate. All patients participating in this trial will receive active therapy for their RA.

Currently, the UK NICE guidelines suggest patients are offered first-line treatment with cDMARD monotherapy using oral methotrexate, leflunomide or sulfasalazine as soon as possible and ideally within 3 months of onset of persistent symptoms. Half of patients in this trial will be randomised to the placebo arm which will be administered in combination with methotrexate therapy.

Abatacept in combination with methotrexate, is indicated for (1) the treatment of moderate to severe active rheumatoid arthritis (RA) in adult patients who responded inadequately to previous therapy with one or more disease-modifying anti-rheumatic drugs (DMARDs) including methotrexate (MTX) or a tumour necrosis factor (TNF)-alpha inhibitor, and (2) the treatment of highly active and progressive disease in adult patients with rheumatoid arthritis not previously treated with methotrexate. In the UK, abatacept in combination with methotrexate is recommended as an option for treating rheumatoid arthritis, only if disease is severe, that is, a disease activity score (DAS28) greater than 5.1, and the disease has not responded to intensive therapy with a combination of conventional disease-modifying antirheumatic drugs (DMARDs). The recommended dose of SC abatacept is 125 mg weekly, regardless of weight. In this trial, half of patients will be randomised to receive abatacept in combination with methotrexate as their first-line therapy.

All patients will undergo synovial biopsies, either US-guided or arthroscopic. These biopsies would not usually be considered routine clinical care. The risks for this type of intervention are small but may include possible infection, bleeding, pain and swelling after the biopsy, and damage to the surrounding tissue such as nerves, tendons or connective tissues. These risks are rare, and the procedure is very well tolerated in most patients. The procedure itself has excellent safety and tolerability and can be applied to both large and small joints as previously demonstrated. The type of biopsy technique performed will be documented for all

participants. Sites with sufficient training and experience in synovial biopsies, will be selected to participate.

Potential Risk of Biopsy:

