- j. A chest X-ray must be performed as screening for tuberculosis prior to biological therapy. A chest x-ray must be done at the screening visit to confirm the patient's eligibility unless a chest X-ray has been done in the preceding 3 months of the screening visit and the patient must not have had any pulmonary symptoms since then. The total protocol dose is less than 0.03mSv. This is equivalent to a few days of average natural background radiation in the UK.
- k. A pregnancy test will be performed at each study visit for female patients of childbearing age irrespective of the use of contraceptive methods.
- I. Joint assessments and VAS physician assessments to be completed by the nominated 'blinded joint assessor'. Joint assessments and VAS physician assessment are only required to be completed by the blinded joint assessor from the baseline visit onwards.
- m. Visit 2 (biopsy visit) may be combined with the completion of visit 1 (study screening visit) if all screening procedures and results are available prior to the biopsy, and the patient is confirmed eligible for enrolment into the study. Sites should contact the coordinating office before arranging.

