## 7.6.4 Disease Activity Score (DAS28) and Clinical Disease Activity Index (CDAI)

The components of the DAS28 are the number of tender joints (28 joint count, **TEN28**), the number of swollen joints (28 joint count, **SW28**), the Patient Global Health Index Score (100 mm VAS, **GH**), and the CRP (in mg/L) for DAS28 (CRP) or ESR (in mm/hr) for DAS28 (ESR).

The formulae for determining the DAS28 are as follows:

DAS28 (CRP) =  $0.56*\sqrt{(TJC28)} + 0.28*\sqrt{(SJC28)} + 0.36*\ln(CRP+1) + 0.014*GH(VAS) + 0.96$ 

DAS28 (ESR) = 0.56\*√(TJC28) + 0.28\*√(SJC28) + 0.7\*ln(ESR) + 0.014\*GH

DAS28 values >5.1 correspond to a high disease activity; values between 3.2 and 5.1 indicate moderate disease activity; values between 2.6 and 3.2 define low disease activity, and values < 2.6 represent remission.

Clinical response will be assessed according to the EULAR response criteria as summarised by the table below.

	DAS28 Improvement		
	> 1.2	> 0.6 and ≤ 1.2	≤ 0.6
≤ 3.2	Good response	Moderate response	No response

	> 3.2 and ≤ 5.1	Moderate response	Moderate response	No response
Present DAS28	> 5.1	Moderate response	No response	No response

The components of the CDAI (Clinical disease activity Index) are tender joints (28-joint count), the number of swollen joints (28-joint count), a Patient global health index (10 cm VAS) and physician global health index (10 cm VAS). This provides an assessment of RA disease activity on a scale from 0-76.

CDAI scores:

- High disease activity: >22
- Moderate disease activity:  $10 < CDAI \le 22$
- Low disease activity  $2.8 < CDAI \le 10$
- Remission  $\leq 2.8$

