#### 14.2 Planned recruitment rate

This study will include at least 10 recruiting centres and recruitment rates at each centre will be reviewed at regular 3TR RA working group meetings. If the recruitment rate is slower than expected, additional centres and PIC sites may be set up in order to meet the recruitment target.

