#### 14.7 Primary endpoint analysis

The primary analysis is within the abatacept arm. It will assess the difference in the change in Clinical Disease Activity Index (CDAI) score at 16 weeks between the biomarker positive and the biomarker negative patients (i.e. Group 1 vs Group 3). This analysis will be on an ITT basis according to original randomisation allocation. The primary outcome will be analysed by analysis of covariance (ANCOVA) with treatment as a factor and baseline value as continuous covariate. If assumptions for ANCOVA are not met, non-parametric ANCOVA will be used. The treatment effect will be reported as least squares mean with 95% confidence intervals.

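### The primary ANCOVA has no site term, although it compares non-randomised biomarker classes across sites with local assessors and local care; depending on inputs the protocol does not give, type I error could lie between about 5% and 8-9%

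*Protocol*

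**What the plan says.** - **Who scores.** Protocol 7.3 states that "each site will have a nominated joint assessor". Note l to the schedule in 7.2 has "Joint assessments and VAS physician assessments to be completed by the nominated" blinded joint assessor, from the baseline visit onwards, and 7.6.5 gives the physician global to the same person. By 7.6.4, CDAI is the tender count (28), swollen count (28), patient global (10) and physician global (10). The assessor therefore supplies three of four components, up to 28 + 28 + 10 = 66 of 76 points.
- **How many sites.** Section 14.2: "This study will include at least 10 recruiting centres". More may be added.
- **What is compared.** Sections 2.1, 14.1 and 14.7 set the primary comparison as Group 1 against Group 3, that is, biomarker-positive against biomarker-negative patients who all receive abatacept.
- **How patients are allocated.** Section 7.3 describes simple 1:1 randomisation to drug or placebo within biomarker class. Site is not a stratification factor.
- **The model.** Sections 14.4 and 14.7 both give an ANCOVA "with treatment as a factor and baseline value as continuous covariate". Treatment is constant within the abatacept arm, so the factor must mean biomarker group. No site, centre or assessor term is named. Section 14.11 allows only exploratory adjustment for imbalanced baseline factors.
- **What limits the problem.** Site staff "they will be blinded to any information about the patient's biopsy result" (7.3). Section 7.5.2, note c, asks for the same assessor at all visits from baseline where possible.

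**The concern.** In an ordinary treatment comparison, randomisation protects against site confounding. It does not do so here, because biomarker class is an observed characteristic and the allocation scheme cannot balance site between Groups 1 and 3.

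Patients at one site share an assessor's scoring habits. They also share local care: methotrexate is prescribed under local guidelines (11.1) and steroids are at the treating clinician's discretion (11.15.3). If the share of biomarker-positive patients also differs between sites, errors are correlated within site and the group variable is correlated with site. An ANCOVA with independent errors then gives too small a standard error, and a site difference can pass for a biomarker effect.

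Different prevalence between sites is plausible but not documented. Recruitment is international (2.7), the technique varies ("All patients will undergo synovial biopsies, either US-guided or arthroscopic", 1.3), and any of eight joint types may be biopsied (2.6).

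**Working it through.** **1. The plan's own figure.** Inputs from 14.1: difference 10, SD 14.34, 90% power. Two-sided 5% is assumed, in line with the 95% intervals in 14.7.

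n per group = 2 × (1.960 + 1.282)² × 14.34² / 10² ≈ 43.2, so 44. Groups 1 and 3 need 88 and the whole trial 176; 176 / 0.90 = 195.6, so 196. The protocol's figures reproduce, and this point does not affect them.

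**2. Approximate type I error without a site term.** Let K be the number of sites, m = 88/K patients per site, ρy the site share of residual variance in week-16 CDAI, and ρx the site clustering of biomarker status. The protocol gives neither ρy nor ρx, so both are assumptions.

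α = 2 × [1 − Φ(1.96 / √(1 + (m − 1) ρy ρx))]

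Example: K = 10, m = 8.8, ρy = 0.10, ρx = 0.2. The variance factor is 1 + 7.8 × 0.02 = 1.156, its root is 1.075, 1.96 / 1.075 = 1.823, and α = 6.8%.

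| K | ρy | ρx = 0 | 0.1 | 0.2 | 0.3 |
|---|---|---|---|---|---|
| 10 | 0.02 | 5.0% | 5.2% | 5.4% | 5.5% |
| 10 | 0.05 | 5.0% | 5.5% | 5.9% | 6.4% |
| 10 | 0.10 | 5.0% | 5.9% | 6.8% | 7.8% |
| 20 | 0.05 | 5.0% | 5.2% | 5.4% | 5.6% |
| 20 | 0.10 | 5.0% | 5.4% | 5.8% | 6.2% |

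Both quantities must be above zero. Site differences alone do not inflate the error.

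**3. Simulation of the stated ANCOVA.** 88 patients, 10 unequal sites, 6,000 runs per setting (Monte Carlo standard error about 0.3 points), and an assumed correlation of 0.5 between baseline and week 16.

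| Site effect | ρx = 0 | 0.1 | 0.2 | 0.3 |
|---|---|---|---|---|
| Arises after baseline, ρy = 0.05 | 5.2% | 5.8% | 6.4% | 6.6% |
| Arises after baseline, ρy = 0.10 | 4.9% | 6.4% | 7.0% | 8.7% |
| Constant assessor offset at both visits, site share 0.10 | 4.6% | 5.2% | not run | 6.2% |
| Constant assessor offset at both visits, site share 0.20 | 5.3% | 5.6% | not run | 6.8% |

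With site as a fixed effect, type I error was 4.5-5.4% in every setting run.

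**4. Random site intercept.** 88 patients, 10 unequal sites, site effect on the response, 1,500 runs per setting. A prevalence SD of s around 50% corresponds to ρx = s² / 0.25, so 0.15 gives 0.09 and 0.25 gives 0.25.

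| Site share | Prevalence SD | Type I, plain | Type I, random site | Power, plain | Power, random site |
|---|---|---|---|---|---|
| 0.10 | 0.15 | 6.2% | 5.1% | 89.2% | 89.9% |
| 0.10 | 0.25 | 7.5% | 5.2% | 86.3% | 86.0% |
| 0.15 | 0.15 | 6.5% | 5.3% | 88.6% | 91.3% |
| 0.15 | 0.25 | 8.4% | 4.7% | 84.6% | 86.6% |

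**5. Power with fixed site effects.** The within-site share of biomarker variance is w = (1 − 1/m)(1 − ρx). The noncentrality is 10 / (14.34 × √(4 / (88w))) on 88 − 10 − 2 = 76 degrees of freedom. At ρx = 0, w = 0.886 and power is 86%; at ρx = 0.1, 0.2 and 0.3 it is 82%, 78% and 72%. These figures allow for no gain from a smaller residual SD.

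**The case against.** **The SAP may deal with it.** Section 14.4 gives the model in brief and leaves detail to the SAP, and nothing excludes a site term. The SAP may well add one. But the protocol states its primary model twice, with its factor and covariate, and an SAP that follows it as written would omit site. The point is about a stated model, not about silence.

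**A reader might infer that assessor scoring alone lifts the error rate to 6-8%.** The documents do not support that. A scoring habit carried by one person appears at baseline and at week 16, and baseline CDAI removes part of it. With offset shares of 0.05-0.15 and prevalence SDs of 0.15-0.25, a further check of 6,000 runs gave 4.9-6.2% with 10 sites and 4.5-5.4% with 20. The higher rates need site effects that arise after baseline. Assessors are also blind to the biopsy result. That removes differential scoring within a site, but not differences between sites.

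**A reader might also take site and assessor to be identical.** Section 7.5.2 asks for the same assessor only where possible, and 7.5.4 speaks of a member of the local team, so a site may use more than one.

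**Uneven biomarker prevalence is unproven.** This stands. Classification uses a central laboratory (9.1) and a single cut-off, the PEAC median (14.1). No passage says that technique or joint shifts the class. A prevalence SD of 0.25 around 50% is extreme: under a beta distribution, 95% of sites would lie between about 6% and 94% positive. With 1,500 runs, the 6.2% has a 95% interval of about 5.0-7.4%.

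**A random intercept is not a full cure.** This also stands. It assumes that site effects are unrelated to site prevalence, and it does little against a constant offset.

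**Conclusion.** The point holds as a cheap improvement. The primary contrast is not randomised, local staff supply most of the CDAI score, local care can differ, and the stated model ignores site.

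The possible type I error runs from about 5% to 8-9%. The top of that range needs about 10 sites, a site share of variance near 0.10 or above that arises after baseline, and strong clustering of biomarker status. A constant assessor offset gives mostly 5-6%, up to about 7%. Even prevalence across sites, or a small site share, gives little or no inflation; having more sites also reduces it. None of these inputs is in the protocol, so no single figure can be assigned to this trial.

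**What to change.** In 14.4 and 14.7, state the primary model as biomarker group, baseline CDAI and a random site intercept. Naming biomarker group also corrects the reference to treatment as the factor within a single treatment arm. Add a fixed-site model, with small sites pooled, as a named sensitivity analysis, because a random intercept does not fully remove systematic site confounding. The fixed-site model should not be primary, since it could cost appreciable power (step 5 of the working).

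The cost is a sentence or two of analysis text and one extra variance parameter, estimated from about 10 sites. In the simulations, power with the random intercept was within about 1 point of the plain model or up to about 3 points higher.

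Extending the term to the secondary comparison (Groups 1 minus 2 against Groups 3 minus 4) is optional. Treatment is randomised within biomarker class there, so site is balanced in expectation.
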